4.6.4 Summary of Safety Monitoring

Safety monitoring in this Phase 2/3 study occurs through several mechanisms:

- Continuous review of safety events by the medical staff involved in the study.
- Protocol Safety Review Committee (PSRT) who will monitor the study's safety events on a routine basis (generally weekly).
- Mechanism to pause further injections if certain safety events occur.
- DSMB to determine if, after evaluation of an initial cohort of 300 subject's immunogenicity and safety from Phase 2, it is advisable to continue with the study.

5 Study Enrollment and Withdrawal

5.1 Description of Subjects, Source of Subjects

Approximately 1800 healthy male and female adults, 18 to 60 years of age.

5.2 Subject Inclusion Criteria

The following criteria must be met before a subject may be enrolled for participation:

- Male or female adult 18 through 60 years of age at the enrollment visit.
- Literate (by self-report) and willing to provide written informed consent.
- Healthy adults, as established by the medical history and screening evaluations, including physical examination, capable and willing to complete Diary Cards, and willing to return for all follow-up visits.
- For females able to become pregnant, willing to utilize reliable birth control measures (intrauterine device, hormonal contraception, condoms) through the Day 43 visit.

5.3 Subject Exclusion Criteria

Subjects meeting any of the following criteria will be excluded from participation:

- Participation in another clinical trial involving any vaccine or therapy within the previous three months, or planned enrollment in such a trial during the period of this study.
- Receipt of any non-study vaccine within 4 weeks prior to enrollment or refusal to postpone receipt of such vaccines until after the Day 43 visit.
- Current or recent (within 2 weeks of enrollment) acute illness with or without fever.
- Receipt of immune globulin or other blood products within 3 months prior to study enrollment or planned receipt of such products prior to the Day 43 visit.
- Chronic administration (defined as more than 14 consecutively-prescribed days) of immunosuppressants or other immune-modulating therapy within six months prior to study enrollment. (For corticosteroids, this means prednisone or equivalent, ≥ 0.5 mg per kg per day; topical or intranasal steroids are allowed.)
- History of asthma.
- Hypersensitivity after previous administration of any vaccine.
- Suspected or known hypersensitivity to any of the study vaccine components, including chicken or egg protein, antibiotics, and rubber (from the vaccine vial stoppers).
- Acute or chronic clinically significant pulmonary, cardiovascular, hepatobiliary, metabolic, neurologic, psychiatric, or renal functional abnormality, as determined by medical history, physical examination, or clinical laboratory screening tests, which in the opinion of the investigator, might interfere with the study objectives.
- History of any blood or solid organ cancer.
- History of thrombocytopenic purpura or known bleeding disorder.
- History of seizures.
- Known or suspected immunosuppressed or immune deficient condition of any kind.

- Known HBV or HCV infection by self-report (Phase 3) or a positive test for either Hepatitis B virus surface antigen (HBsAg) or HCV antibody using anti-HCV test (Phase 2).
- Known HIV infection (self-report)
- Known active tuberculosis or symptoms of active tuberculosis (self-report).
- History of chronic alcohol abuse and/or illegal drug use.
- Pregnancy or lactation (a negative pregnancy test will be required before administration of study product for all women of childbearing potential).
- History of Guillain-Barre Syndrome.
- Any condition in the opinion of the investigator that would increase the health risk of the subject if he/she participates in the study or interfere with the evaluation of the study objectives.

Note: Minor out-of-range laboratory values no greater than Grade 1 (see toxicity table in Appendix) will not be considered to be exclusionary at screening.

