3.2 Outcome Measures

3.2.1 Primary and Secondary Immunogenicity Endpoints

Primary Immunogenicity Endpoints (Phase 2 and Phase 3): Immunogenicity Measures will Include:

- Percentage of subjects achieving an HAI titer $\geq 1:40$ after the second vaccination on Day 43.

[Note: this endpoint is equivalent to another commonly used endpoint of seroconversion as defined as prevaccination titer $< 1:10$ and a post-vaccination titer $\geq 1:40$ OR significant increase in antibody titer (a

pre-vaccination titer of $\geq 1:10$ and at least a four-fold increase in post-vaccination titer), since all subjects are expected to have baseline titer of $< 1:10$.]

Dose Selection Criteria for Phase 3: The higher vaccine dose tested (30 mcg) will be selected if it induces higher immune responses than the lower dose as described in the table below. Other factors such as safety and manufacturing costs will also be considered.

Dose	Percentage of subjects with HAI ≥ 40 after two vaccinations			
Low dose (15 mcg)	< 60%	60-64%	65-74%	$\geq 75\%$
High dose (30 mcg)	≥ 60	> 15 mcg dose	$> 13\%$ higher	Any
Dose selection	30 mcg	30 mcg	15 mcg, if $\Delta < 13\%$	15 mcg
			30 mcg if $\Delta \geq 13\%$	

Note Δ represent a difference in HAI in the high and low dose groups.

Success Criterion for Phase 3: the selected dose of vaccine induces responses in 60% or more of the approximately 300 subjects receiving the IVACFLU-A/H5N1 (vaccinees) selected for HAI immunogenicity testing.

Secondary Immunogenicity Endpoints: Immunogenicity Measures will Include:

Phase 2 (HAI and MN testing in all 300 Phase 2 subjects)

- Percentage of subjects with a serum HAI titer $\geq 1:40$ at Day 22.
- Percentage of subjects demonstrating an HAI seroresponse of at least a four-fold increase in post-vaccination titer on Day 22 and Day 43.
- Percentage of subjects with at least a four-fold rise in titer at Day 22 and Day 43, as determined by microneutralization (MN).
- Geometric Mean Titer (GMT) of Day 22 and Day 43 as determined by the HAI and MN tests.
- Geometric Mean Titer Ratio (GMTR) of Day 22/Day 1 and Day 43/Day 1 as determined by the HAI and MN tests.

Phase 3 [HAI testing in approximately 300 subjects receiving the IVACFLU-A/H5N1 (vaccinees); MN testing to be determined based on the results from Phase 2]

- Percentage of subjects demonstrating an HAI seroresponse of at least a four-fold increase in post-vaccination titer on Day 43.

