4.2 Study Sites

Phase 2 of this study will be conducted at one clinical site in one province and Phase 3 will be conducted in three provinces in Vietnam.

Phase 2

The Phase 2 part of this study will be conducted in the Khanh Hoa Province at Ninh Hoa District Health Center. Data entry/CRF storage will be at the Khanh Hoa Provincial Health Department.

Phase 3

The Phase 3 part of the study will be conducted at three provinces, as follows:

1. Khanh Hoa Province: (same site as Phase 2, but study activities move to the communes)
 - Study activities at the Ninh Da, Ninh Binh, and Ninh Quang Commune health centers.
 - Data entry/CRF storage at the Khanh Hoa Provincial Health Department.
2. Hai Phong Province:
 - Study activities at the Cap Tien, Kien Thiet, and Hung Thang Commune health centers.
 - Data entry/CRF storage at the Hai Phong Preventive Medicine Center.
3. Hoa Binh Province:
 - Study activities at the Hop Kim, Nam Thuong, and Thuong Bi Commune health centers.
 - Data entry/CRF storage at the Hoa Binh Preventive Medicine Center.

For Phase 3, study documents will be stored at the provincial level where data entry will occur, and will be moved to the particular commune health center when a study visit is occurring there.

These locations were satellite sites for several vaccine clinical trials conducted in collaboration with National institute of Hygiene and Epidemiology (NIHE). The staff of the district health center, as well as the staff of the provincial centers in the three provinces have experience in implementing vaccine trials and observational studies on various infectious diseases. They also have experience in working with contract research organizations (CROs), and with local and international sponsors.

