Kitasato Institute, Japan	Al(OH)3	1.7, 5, 15	Two doses at day 0, 21	No data	NT \geq 4 fold increase after 2 doses: IM SC 100% 74% (15 μ g+Alum) 75% 58% (5 μ g+Alum) 50% 25% (1.7 μ g+Alum)	Fold Increase in NT after 2 doses: SC 41.5 (15 μ g+Alum) 29.9 (5 μ g+Alum) 12.7 (5 μ g+Alum)
Kitasato Institute, Japan	Al(OH)3	5, 15	Two doses at day 0, 21	No data	NT \geq 4 fold increase after 2 doses: 81% (15 μ g+Alum) 65% (5 μ g+Alum)	Fold increase in NT after 2 doses: 5.1 (15 μ g+Alum) 3.7 (5 μ g+Alum)
Kaketsuken, Japan	Al(OH)3	1.7, 5, 15	Two doses at day 0, 21	NT \geq 40 after 2 doses: IM SC 45% 37% (15 μ g+Alum) 20% 5% (5 μ g+Alum)	NT \geq 4 fold increase after 2 doses: IM SC 75% 68% (15 μ g+Alum) 50% 20% (5 μ g+Alum)	Fold increase in NT after 2 doses: IM SC 6.3 4.8 (15 μ g+Alum) 2.9 1.6 (5 μ g+Alum)
Kaketsuken, Japan	Al(OH)3	5, 15	Two doses at day 0, 21	NT \geq 40 after 2 doses: 77% (15 μ g+Alum) 53% (5 μ g+Alum)	NT \geq 4 fold increase after 2 doses: 86% (15 μ g+Alum) 56% (5 μ g+Alum)	Fold increase in NT after 2 doses: 8.9 (15 μ g+Alum) 4.3 (5 μ g+Alum)
Biken and Kitazato Institute, Japan	Al(OH)3	15	Two doses at day 0, 21	NT \geq 40 after 2 doses with Indonesia against: Indonesia Vietnam 74% 15%	NT \geq 4 fold increase after 2 doses with Anhui Ag against: Anhui Vietnam 82% 74%	Fold increase in NT after 2 doses with Indonesia against: Indonesia Vietnam 9.4 2.0
Biken and Kitazato Institute, Japan	Al(OH)3	15	Priming: two doses with Vietnam strain; Booster: single dose two years after priming	NT \geq 40 after boosting with Indonesia against: Indonesia Vietnam 92% 97%	NT \geq 4 fold increase after boosting with Anhui Ag: against: Anhui Vietnam 94% 1%	Fold increase in NT after boosting with Indonesia: against: Indonesia Vietnam 36.7 23.1
Biken and Kitazato Institute, Japan	Al(OH)3	15	Two doses at day 0, 21	No data	No data	No data

Producer	Adjuvant	Dose	Schedule	% Responders at a Specified Titer	Seroconversion Rate	GMT Increase

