Analysis Population: All immunogenicity endpoint analyses and summaries will be performed on a per-protocol basis for all subjects and by age group (18-40 years of age and 41-60 years age). Supportive analysis will also be conducted on participants in the FA population who received at least one dose of study vaccines if the difference in the number of subjects between the FA and PP populations exceeds 5%.

Study Endpoints

Primary:

- Percentage of subjects achieving an HAI titer $\geq 1:40$ after the second vaccination on Day 43

Secondary:

- The percentage of subjects achieving a seroresponse (at least a four-fold increase in post-vaccination titer) on Day 43 as determined by HAI
- Geometric Mean Titer (GMT) of Day 43 as determined by HAI.

³ Horne AD, Lachenbruch PA, Getson PR, and Hsu HS Analysis of Studies to Evaluate Immune Response to Combination Vaccines. Clinical Infectious Diseases 2001; 33(Suppl 4):S306-11

- Geometric Mean Titer Ratio (GMTR) of Day 43/Day 1 as determined by HAI.

Analysis Methods

There are two types of immunogenicity measurements, percentages of subjects with immune response and Geometric Mean Titers (GMT), that will be used to evaluate this study objective.

Percentages of subjects with immune response:

- Percentage of subjects achieving an HAI titer $\geq 1:40$ ⁴ on Day 43.
- Percentage of subjects demonstrating an HAI seroresponse of at least a four-fold increase in postvaccination titer on Day 43.

For each percentage of subjects with the defined immune responses, the percentage and its corresponding 2-sided exact (Clopper-Pearson) binomial 95% confidence interval (95% CI) around the percentage will be computed for each treatment group and by age group.

Geometric Mean Titers (GMTs):

- Geometric Mean Titer (GMT) of Day 43 as determined by HAI
- Geometric Mean Fold Rise (GMFR): Geometric Mean of Titer Ratio of Day 43/Day 1 as determined by HAI.

GMT along with the corresponding two-sided 95% CIs, by exponentiating the corresponding log-transformed means and their 95% CIs, will be summarized by treatment group on Day 1 and Day 43. The same approach will be used to summarize GMFR of Day 43/Day 1 separately by treatment group and age group.

Furthermore, the analyses will be repeated by combining the immunogenicity measures of the selected dose group and the placebo group from both Phases 2 and 3 cohorts if needed. No comparisons will be made between the IVACFLU-A/H5N1 dose group and the placebo group.

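### Section 5.3 does not exclude Phase 2 participants or earlier H5N1 vaccinees from Phase 3, so a person could re-enrol and be counted twice in pooled safety; the effect is modest and the fix cheap

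*Protocol*

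**What the plan says.** Two entries in Protocol 5.3 bear on prior exposure. One excludes "Participation in another clinical trial involving any vaccine or therapy within the previous three months"; the other excludes "Receipt of any non-study vaccine within 4 weeks prior to enrollment". A closing entry leaves room for judgement: "Any condition in the opinion of the investigator that would increase the health risk of the subject", or that would interfere with evaluating the objectives. No entry names an earlier H5N1 vaccine, Phase 2 of this study, or a baseline titre. The medical history in 8.1.3 asks about recent vaccination only.

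Lack of prior immunity is assumed, not required. The note in 3.2.1 equates the primary endpoint with seroconversion "since all subjects are expected to have baseline titer of" less than 1:10. The final SAP (section VII footnote) adds a seroconversion analysis if any subject starts at 1:10 or above.

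The two phases share ground. Section 4.2 lists Khanh Hoa in Phase 3 as the "same site as Phase 2, but study activities move to the communes". Of the study locations generally it says "These locations were satellite sites for several vaccine clinical trials", without naming the vaccines. Section 4.4 puts the break between phases at 8 to 10 months; 9.5.2 puts the pause at about 6 months.

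The phases may also be combined. Section 12.2 bases its safety precision on about 1100 recipients of the selected dose across both phases. The final SAP allows "combining the immunogenicity measures of the selected dose group and the placebo group from both Phases 2 and 3 cohorts" where needed (section VII), and the same for safety (section VIII).

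**The concern.** Both windows run out during the break, so an earlier participant passes them. The word "another" in the trial criterion may not reach Phase 2 at all, since Phase 2 is part of this same trial. Subject numbers are not reused (5.4.1) and no identity check across phases is described, so a returning person would enter the database as a new subject.

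Two consequences follow in principle. A returning selected-dose recipient would count as two people in the pooled safety denominator, and the second record would describe someone who has had more than the two-injection course under study. Separately, the Phase 3 success rule is an observed rate of at least 60% in vaccinees, with no comparison against placebo. Randomisation therefore does not cancel the effect of any vaccinees who were already primed.

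**Working it through.** **Do the windows lapse?** The shortest interval in the documents is the 6-month pause in 9.5.2, counted from the second injection (Day 22). Phase 2 follow-up ends at Day 91, which is 69 days or about 2.3 months later. That leaves about 6 − 2.3 = 3.7 months, still more than three. With the 8 to 10 months in 4.4 the margin is wider.

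**The plan's own figures.**
- Exact 95% upper bound with zero events in 1100: 1 − 0.025^(1/1100) = 0.335%. The protocol gives 0.33%.
- Chance of at least one event at a true rate of 0.21%: 1 − (1 − 0.0021)^1100 = 90.1%. The protocol says greater than 90%.
- Chance of at least 180 responders in 300: 96.9% at a true rate of 65% and 99.99% at 70%. The protocol says 97% and more than 99%.

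All reproduce.

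**Double counting in pooled safety.** Let d be the number of selected-dose Phase 2 subjects who re-enter the Phase 3 vaccine arm. The number of distinct people is N − d, and the zero-event bound is 1 − 0.025^(1/(N − d)). The most d can be is 100.

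| Sizes | N | d | Distinct people | Upper bound | Chance of ≥1 event at 0.21% |
|---|---|---|---|---|---|
| Protocol (100 + 1000) | 1100 | 0 | 1100 | 0.335% | 90.1% |
| Protocol | 1100 | 67 | 1033 | 0.356% | 88.6% |
| Protocol | 1100 | 100 | 1000 | 0.368% | 87.8% |
| Final SAP (100 + 500) | 600 | 0 | 600 | 0.61% | 71.7% |
| Final SAP | 600 | 100 | 500 | 0.74% | 65.0% |

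The row d = 67 is what 2:1 randomisation would give if all 100 returned (100 × 2/3). The rows with d = 100 are the extreme case.

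**Primary HAI rate.** Phase 2 ran in Khanh Hoa. Phase 3 HAI is measured only in Hai Phong (Protocol Summary; final SAP Preface). A person who returns in Khanh Hoa is not in the HAI subset. The only remaining route is a person in Hai Phong vaccinated against H5N1 in some other trial. Let f be the share of such people, p the naive rate and q the primed rate. The expected rate is p + f(q − p). The documents do not give f, so the values below are assumptions. The table shows the chance of at least 135 responders in the SAP's 225 vaccinees.

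| p | f = 0 | f = 5%, q = 79% | f = 5%, q = 90% | f = 5%, q = 95% |
|---|---|---|---|---|
| 56.3% (Phase 1, 15 mcg, 18/32) | 14.6% | 23.9% | 29.4% | 32.1% |
| 58% (assumed) | 29.5% | 41.4% | 48.0% | 51.1% |
| 65% (lower planning rate in 12.3) | 94.9% | 96.8% | 97.9% | 98.3% |

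Example: 0.58 + 0.05 × (0.90 − 0.58) = 0.596, which gives 48.0%. With f = 1% and q = 90% at p = 58%, the chance moves only from 29.5% to 33.0%.

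The range for q is guided by Appendix A. The row "Priming: two doses with Vietnam strain; Booster: single dose two years after priming" reports 92% and 97% reaching a neutralisation titre of 40 after the booster. Another manufacturer's rows give HI titres of 40 or more after a booster in 79% at 5 mcg and 90% at 10 mcg, against 93% and 100% by neutralisation. The trial's endpoint is HAI, so the lower values are the closer guide. All come from other products.

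**The case against.** The strongest reply is that little can go wrong in practice.

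- **Sites.** The final SAP has two Phase 3 sites and names only Hai Phong. If the other is not Khanh Hoa, a returning Phase 2 subject becomes unlikely. This stands, though the SAP does not settle it.
- **Analysis.** The confirmatory analysis uses Phase 3 data alone (Protocol 28.2; final SAP V), and pooling is optional. This limits the double-counting point to supportive tables and to the 1100 in 12.2.
- **Existing safeguards.** Investigator discretion, the vaccination history and the blinded review of Per Protocol exclusions could catch some cases. So it would be too much to say that nothing excludes such people. None of these names the condition, however, and none triggers a check.

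A reader might infer that returning Phase 2 vaccinees would inflate the primary HAI rate. The documents do not support that, because the HAI subset is drawn only from Hai Phong. A reader might also take the rise from 30% to 51% (5% primed), or to 72% (10% primed), at p = 58% and q = 95% as the expected bias. Those figures are arithmetically right, but they need a naive rate set just below 60%, a neutralisation-test response in place of HAI, and 11 to 23 primed people among 225. Section 2.1.1 says no H5N1 vaccine is licensed in Vietnam. It mentions another manufacturer's completed Phase 3 trial but gives neither its size nor its place. Nothing puts an H5N1 vaccinee in Hai Phong.

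Nor do the documents show that primed people would start below 1:10 and then boost: the Appendix A booster rows give no pre-booster titres. What can be said is that the SAP's added seroconversion analysis would not flag such a person.

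**Conclusion.** The gap in 5.3 is real, and its likely effect is modest. Under the protocol's site list, a Phase 2 subject could enrol again in Khanh Hoa, receive a second course and be counted twice in pooled safety. In the extreme case of all 100 selected-dose subjects returning to the vaccine arm, the zero-event upper bound moves from 0.33% to 0.37% on protocol sizes and from 0.61% to 0.74% on final SAP sizes. The chance of seeing a 0.21% event on protocol sizes falls from 90% to 88%.

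For the primary endpoint the documents support only a conditional statement. The 60% criterion could be biased upward by earlier H5N1 trial vaccinees in Hai Phong. Their share is unknown, at zero there is no bias, and it matters only if the naive rate is near or below 60%. At 65% the chance of success is already 95% with nobody primed.

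**What to change.** - Add to 5.3 an exclusion for earlier participation in this study (either phase) or earlier receipt of any H5N1 vaccine.
- Apply it with one screening question and a check against the Phase 2 screening and enrolment log, which already holds name and date of birth (5.4.1). The log as described there carries no allocation, so the check does not touch the blind.
- In the final SAP, list the same condition as a Per Protocol exclusion, set before unblinding.
- In any table that pools the phases, count each person once and report any repeat enrolment separately.
- Name the second Phase 3 site in the SAP, so that the possibility of overlap is settled.

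If Phase 3 enrolment has already closed, the log comparison and the last three items can still be done before unblinding.

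This is a cheap improvement. It costs one question, a log check and a few lines of text, and a few otherwise eligible people would be turned away.

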5.4 Treatment Assignment Procedures

5.4.1 Randomized Procedure

This is a double-blind, randomized, and controlled trial with a 1:1:1 ratio among three groups in Phase 2: 15 mcg/mL vaccine, 30 mcg/mL vaccine, and placebo; and 2:1 ratio between two groups in Phase 3: either 15 mcg/mL or 30 mcg/mL vaccine and placebo. Each subject will be assigned a unique screening number by the investigator after signing the informed consent.

The Investigator will maintain the screening/enrollment log. The log will contain essential information including subject name, date of screening, gender, date of birth, whether or not the subject meets eligibility criteria, whether subject is enrolled and date, and if not enrolled, reason why the subject is not enrolled or not randomized.

Once a subject identification number has been assigned to a subject, it will not be used again. Additional subjects may be randomized into the study at the discretion of the sponsor in the case of any subject who is randomized but does not receive any study vaccine.

The permuted randomization block design procedure will be used to generate the randomization schedules for both Phase 2 and Phase 3. The randomization will be stratified by province and age group (18-40 years of age and 41-60 years age). The block size for each part will be chosen based on the number of treatment groups and anticipated enrollment sizes at each province.

5.4.2 Blinding and Unblinding Procedures

The mechanics of randomization will be conducted by an entity that is not involved with trial follow-up or monitoring. Details of the mechanics of randomization will not be provided in the protocol or to any staff implementing the trial in order to assure integrity of the data.

The randomization lists for subjects will be used by IVAC to label study vaccine and placebo vials, and then will be immediately sealed. It will be opened only after the clinical trial database is declared

complete and locked. In the case of any unblinding, researchers must report this in writing to the sponsor and overseeing Ethics Committee.

IVAC vaccine and placebo vials will be packaged and labeled in such a way that they have similar appearance. However, IVACFLU-A/H5N1 vaccine uses aluminum hydroxide as an adjuvant and the placebo is phosphate buffered saline (PBS), so there will be a slight difference in the appearance between vaccine and placebo. To address the blinding issue, in addition to the original vial label of the vaccine and placebo designed by IVAC in compliance with the drug labeling regulations of the Ministry of Health, an identical study label designed for experimental vaccine and placebo containing only the study product code of each subject will be pasted over the original vial label to ensure implementation of double blinding. The labeling will be done at IVAC before study vaccine and placebo are shipped to the study site. To blind the vaccinator and study subjects, a nurse will be recruited and trained to be responsible for withdrawing study product from vials according the randomization schedule in a separate room/closed private space, then masking the syringe before handing over to vaccinator. A SOP on this procedure will be developed to ensure the double-blind of this study. This nurse will not participate in any safety evaluation of study subjects.

Study product injected into each subject will be recorded using the exact allocation code for each product received by each subject.

The allocation codes which link treatment identification with each subject via subject identification numbers will be maintained in a secure location and managed by individuals who are not directly implementing or monitoring the trial. The allocation code listing will not be opened or linked to the clinical trial database until after all databases are locked. All blinded study staff will remain blinded throughout the trial. If any subject experiences an SAE possibly related to receipt of study treatment, treatment allocation to the subject may be communicated to the investigator only if that information is deemed necessary to properly treat the subject for the SAE. Written procedures for blinding, storage, and opening of study codes, in compliance with the approved protocol, will be developed to ensure the study is not unnecessarily unblinded.

